3.8.1.6 Supportive analyses of the primary endpoint

The following analyses will be conducted in the PIK3CA mutant cohort to support the interpretation of the primary endpoint, regardless of the outcome in the primary endpoint.

- If there is a high rate of discrepancy (>10%) between the strata classifications constructed using CRF data and those obtained from the IRT (considering also PIK3CA mutation status), a sensitivity analysis will be performed in which a stratified Cox regression model will be used to estimate the treatment hazard ratio and the associated 95% confidence interval based on the CRF-derived strata.
- Number of patients with a PFS event and number of patients censored for the PFS analysis will be summarized. In addition, a summary of reasons for PFS censoring will be provided by treatment arm based on the reasons defined in [Section 2.4.5](#).

The following summaries on censoring reasons will be produced for PFS by investigator radiology and central radiology. The censoring patterns will be compared between investigator and central review (in patients selected for BIRC assessment).

- Comparison of PFS event type/censor between local radiology review and central radiology review
- Summary for the difference in days to progression as per local radiology review and as per central radiology review

PFS assessed by Blinded Independent Review Committee (BIRC) will serve as supportive evidence of the primary endpoint in the PIK3CA mutant cohort.

For studies with PFS based on local radiology assessment as the primary endpoint, PFS assessment done centrally has generally been used as a secondary or supportive analysis of the treatment effect observed in the primary efficacy analysis. Although 100% central review of scans has been performed in many trials, there is a growing body of evidence that an audit based approach for central evaluation is sufficient ([Zhang et al, 2012](#), [FDA ODAC 2012](#)).

An audit (sample) based approach will therefore be implemented for the BIRC assessment of PFS, whereby all assessments for a randomly selected subset of randomized patients will be assessed by BIRC. An independent random sampling process, implemented by the third party IRT vendor, will select approximately 50% of randomized patients. This random allocation will be stratified by randomized treatment arm and the strata used for the randomization of patients to treatment arms.

The distribution of PFS based on audit BIRC sample will be estimated using the Kaplan-Meier method for the FAS. The median along with two-sided 95% confidence intervals (CI) will be presented by treatment group. Kaplan-Meier figure will also be displayed. A stratified Cox regression will be used to estimate the hazard ratio (HR), along with two-sided 95% CI based on the audit BIRC sample.

Two additional methods will be used to summarize the data from the BIRC assessment in order to decide whether a 100% BIRC review should be conducted.

- The NCI (National Cancer Institute) method ([Dodd et al. 2011](#)), uses an auxiliary variable estimator of the log-hazard ratio that combines information from patient-level investigator assessment from all patients in the PIK3CA mutant cohort and the BIRC assessment of these patients randomly selected for central review (see [Section 4.8](#) for methodological details). This estimate and its one-sided 95% CI will be provided. The NCI method will be used for audit sample size determination (see [Section 3.14](#)) and summary of treatment effect (HR, 95% confidence intervals) based on the supportive BIRC assessment.
- The data from the BIRC assessment generated following the sampling scheme as above will also be summarized using the method proposed by [Amit et al. 2011](#), referred to as the PhRMA (Pharmaceutical Research and Manufacturers in America) method, based on the early discrepancy rate (EDR) and late discrepancy rate (LDR).

The EDR quantifies the frequency with which the investigator declares progression early relative to BIRC within each arm as a proportion of the total number of investigator assessed PDs. The LDR quantifies the frequency that the investigator declares progression later than BIRC as a proportion of the total number of discrepancies within the arm. If the distribution of discrepancies is similar between the arms this suggests the absence of evaluation bias favoring a particular arm. (see Section 4.8 for details on the calculations). With this approach, the differential discordance (DD) of the early discrepancy rate (EDR) and late discrepancy rate (LDR) between the two arms will be estimated as the rate on the alpelisib+fulvestrant arm minus the rate on the placebo+fulvestrant arm. The EDR and LDR results will also be summarized by treatment arm.

If the analysis of primary endpoint in the PIK3CA mutant cohort shows a statistically significant treatment effect, a full BIRC review may be conducted.

The following thresholds based on the NCI and PhRMA methods will be used to define the trigger for a full BIRC review:

- If the upper-bound of the one-sided 95% confidence interval for BIRC-based log-hazard ratio exceeds zero (i.e. $HR > 1$) based on the NCI method

and/or

- If $\geq 15\%$ differential discordance is observed in EDR or LDR based on the PhRMA method (a negative observed differential discordance for the EDR or a positive differential discordance for the LDR)

Cross-tabulation of ‘PFS by central radiology’ vs. ‘PFS by investigator’ by PFS event type (i.e. ‘death’, ‘PD’, ‘censor’ for each of the two sources) and by treatment will be constructed to investigate discordance between the two sources (in patients selected for BIRC assessment). The discrepancy rate between central radiology and investigator will be calculated and presented as % as follows: $100 \times (n_{13} + n_{23} + n_{31} + n_{32}) / N$ by treatment arm.

A cross-tabulation will be produced displaying the PFS timings for the local investigators' assessment compared to the BIRC assessment (in patients selected for BIRC assessment). For progression assessments, the frequency and percent of subjects with complete agreement [occurring on the same date plus or minus 7 days of each other], progression later, progression earlier, and cases where progression was called by one method and censored by the other will be displayed. Similarly, if censoring was recorded, the frequency and percent of subjects with complete agreement, censoring called later, censoring called earlier, and cases where censoring was called by one method and progression was called by the other method will be displayed.

3.8.1.6.1 Missing tumor assessments

The number of patients with at least one missing/unknown TA based on local assessment will be presented together with the following breakdown categories: number of patients with 1, 2, 3, 4, 5, >5 missing/unknown TAs. The purpose of this analysis is to gain an insight as to whether the TAs have been carried out in accordance with the protocol and to understand if any meaningful discrepancies exist between the pattern of missing assessments by treatment arms.

Since the planned tumor assessments are every 8 weeks in the first 18 months and every 12 weeks thereafter, the following time windows (in weeks) will be constructed for each patient: (note the open parenthesis such as (12, 20] indicates that week 12 doesn't belong to this interval and week 12+1 day belongs to that interval)

- Until ~18 months post randomization [0, 12], (12, 20], (20, 28], ... (60, 68], (68, 76]
- After ~18 months post randomization (76, 90], (90, 102], (102, 114], ...

where '0' is the patient's date of randomization. Every time-window (with the exception of the initial, broader one) is centered at the scheduled time of a TA, i.e., around week 16, week 24 for second and third window respectively, etc. A patient will be considered 'at risk' of missing his/her TA for any one of these time-windows if he/she either:

[figure not shown]
- is 'on study' for at least the first 4 weeks of the time-window for the first 18 months (8 weeks for the first time window), or at least the first 6 weeks of time-window thereafter, i.e., if the patient is ongoing at the time of the scheduled TA, or
- discontinued treatment due to documented disease progression within the specific time window.

For example, if a patient discontinued due to documented disease progression during Week 24, then he/she would have been 'at risk' of a missing/unknown TA for the [20, 28] week time-window.

For the purpose of this analysis, 'unknown' TAs (i.e., evaluations with an overall lesion response of 'unknown') will be considered to be missing. However, a clear distinction between 'truly missing' and 'present but unknown' needs to be made in the derived dataset to allow for both a combined analysis, i.e. missing and unknown treated the same, and separate analyses.

TAs performed after a documented disease progression will not be considered. In other words, the final time-window for which a patient would be at risk of a missing/unknown scan would be that during which the documented progression occurred.

For patients without documented progression, all TAs are considered up to the earliest of the following dates: death, the analysis cut-off, disease progression, withdrawal of consent or loss to follow-up.

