2.4.5 Determination of missing adequate assessments

The term ‘missing adequate tumor assessment’ is defined as a tumor assessment not done or tumor assessment with overall lesion response ‘Unknown’. For the sake of simplicity, a ‘missing adequate tumor assessment’ will also be referred to as a ‘missing assessment’.

As described in Table 14-9 in Appendix 3 of the study protocol, the PFS censoring and event date options depend on the presence and the number of missing tumor assessments (TAs). In the analysis of PFS, an event occurring after two or more missing assessments or non-adequate tumor assessments is censored at the last adequate tumor assessment.

An exact rule to determine whether there is no, one or two missing TAs is therefore needed. This rule is based on the time interval between the last adequate tumor assessment (LATA) date and the event date. The scheduled date of tumor assessments (in weeks from randomization), protocol specified windows for tumor assessments, and the thresholds for LATA to belong to a visit can be found in the following table.

Schedule for tumor assessment and time windows

Assessment schedule		Scheduled date – 1 week	Scheduled date (weeks from randomization)	Scheduled date +1 week	Threshold (weeks)*
Every 8 weeks for the first 18 months	Baseline	0	0^	1	n/a
	C3D1	7	8	9	12
	C5D1	15	16	17	20
	C7D1	23	24	25	28
	C9D1	31	32	33	36
	C11D1	39	40	41	44
	C13D1	47	48	49	52
	C15D1	55	56	57	60
	C17D1	63	64	65	68
	C19D1	71	72	73	78
	C22D1	83	84	85	90

Every 12 weeks after 18 months	C25D1	95	96	97	102
	C28D1	107	108	109	114
	C31D1	119	120	121	126

* The mid-point between current and next visit (except for baseline) and the upper limit for LATA to be matched to a certain scheduled assessment, e.g. if LATA is at week 13, this is after threshold for C3D1 and before that for C5D1, so the matching scheduled assessment is C5D1.

^ Day of randomization is taken as 0.

To calculate the number of missing tumor assessments, the LATA before an event is matched with a scheduled tumor assessment using the time window in the table above (essentially whichever scheduled assessment it is closest to).

Two additional thresholds, D1 and D2 are calculated for that scheduled assessment based on the protocol-specified schedule and windows.

- The threshold D1 is defined as the protocol-specified time interval between the TAs plus 2x the protocol-allowed time window around the assessments.

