- The threshold D2 is defined as twice the protocol-specified time interval between the TAs plus 2x the protocol-allowed time window around the assessments (except when the matched scheduled tumor assessment is C17D1, in which case D2 is defined in Rule 2 below).

Since there is a change of schedule for tumor assessments after 18 months, D1 and D2 are defined differently depending on when LATA occurs.

Rule 1: if LATA happens within 60 weeks from randomization (the matched scheduled tumor assessment is C15D1 or before). For example, D1=8+2=10 weeks and D2=2*8+2=18 weeks.

Rule 2: if LATA happens after 60 weeks but within 68 weeks from randomization (the matched scheduled tumor assessment is C17D1). For example, D1=8+2=10 weeks and D2=8+12+2=22 weeks.

Rule 3: if LATA happens after 68 weeks from randomization (the matched scheduled tumor assessment is C19D1 or later). For example, D1=12+2=14 weeks and D2=2*12+2=26 weeks.

The number of missing events is defined as:

- An event after LATA+D1 weeks will be considered as having ≥ 1 missing assessment
- An event after LATA+D2 weeks will be considered as having ≥ 2 missing assessments

The same definition of D2 will be used to determine the PFS censoring reason. If there is no post-baseline adequate tumor assessment available (before an event or a censoring reason occurred), the randomization date will be used to compute the interval.

If the time interval between the last adequate TA date and the earliest of the following dates is smaller or equal to D2 days:

Analysis cut-off date

Date of consent withdrawal

Visit date of study treatment discontinuation due to lost to follow-up or end of post-treatment follow-up discontinuation due to lost to follow-up.

Then the PFS censoring reason will be respectively:

- ‘Ongoing’
- ‘Withdrew consent’
- ‘Lost to follow-up’

However if the time interval is larger than D2 days with no event then the PFS censoring reason will always default to ‘Adequate assessment no longer available’. If the time interval between the last adequate tumor assessment date and the PFS event date is larger than D2 then the patient will be censored and the censoring reason will be 'Event documented after two or more missing tumor assessments'.

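### SAP 3.8.1.6.1 changes from 8-weekly to 12-weekly missing-scan windows at week 76, while SAP 2.4.5 uses week 78; the week-84 scan can be counted missing before it is due, with a small effect on one descriptive table

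*SAP*

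**What the plan says.** SAP 3.8.1.6.1 describes a table of missing or unknown tumor assessments by arm. Its purpose is to show whether scans followed the protocol and whether the pattern of missing scans differs between arms.

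- The windows, in weeks from randomization, are "Until ~18 months post randomization [0, 12], (12, 20], (20, 28], ... (60, 68], (68, 76"], followed by "After ~18 months post randomization (76, 90], (90, 102], (102, 114"] and so on.
- On their position: "Every time-window (with the exception of the initial, broader one) is centered at the scheduled time of a TA".
- A patient is at risk of a missing scan after 8 weeks of the first window, after 4 weeks of the other 8-weekly windows, and, for the 12-weekly windows, after "at least the first 6 weeks of time-window thereafter, i.e., if the patient is ongoing at the time of the scheduled TA". A patient who stopped treatment for documented progression within the window is also at risk.
- Without documented progression, scans are considered up to the earliest of death, analysis cut-off, withdrawal of consent or loss to follow-up.

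SAP 2.4.5 matches the last adequate tumor assessment (LATA) to a scheduled visit by a threshold, defined as "The mid-point between current and next visit (except for baseline) and the upper limit for LATA to be matched to a certain scheduled assessment". Its table columns are scheduled week minus 1, scheduled week, scheduled week plus 1, and threshold. The two rows at the change of schedule read "C19D1 71 72 73 78" and "C22D1 83 84 85 90".

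**The concern.** The two sections divide the same pair of scans, C19D1 at week 72 and C22D1 at week 84, at different weeks, and the SAP gives no reason. Within 3.8.1.6.1, the window (76, 90] also fits neither the centering statement nor the at-risk rule. Followed literally, that rule starts the risk of missing the week-84 scan before a compliant patient could have had it. A scan at week 77 would count as a late week-72 scan in 2.4.5 but as the week-84 scan in 3.8.1.6.1. If there was no other scan in (68, 76], week 72 would then be shown as missing, and a week-84 scan that really was missed could be hidden.

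What is at stake is the accuracy of a table meant to reveal departures from the scan schedule and differences between arms. The affected window lies late in follow-up, where more alpelisib than control patients are expected to be progression-free, so any false counts would not fall equally on the arms.

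**Working it through.** **Step 1: reproduce the thresholds.** Scheduled weeks from SAP 2.4.5 are 8, 16, 24, …, 64, 72, 84, 96, 108, 120. The mid-points of neighbors are 12, 20, 28, 36, 44, 52, 60, 68, 78, 90, 102 and 114, which match the 2.4.5 thresholds. At the change of schedule, (72 + 84)/2 = 78. The same rule gives every boundary listed in 3.8.1.6.1 except 76. The figure 76 equals 72 + 4, the half-width of an 8-weekly window.

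**Step 2: test the statements in 3.8.1.6.1.** The at-risk point is the window start plus 4 weeks (8-weekly) or 6 weeks (12-weekly).

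| Window | Scan due | Center | At-risk point | Weeks before due |
|---|---|---|---|---|
| (60, 68] | 64 | 64 | 60 + 4 = 64 | 0 |
| (68, 76] | 72 | 72 | 68 + 4 = 72 | 0 |
| (76, 90] | 84 | (76 + 90)/2 = 83 | 76 + 6 = 82 | 2 |
| (90, 102] | 96 | 96 | 90 + 6 = 96 | 0 |
| (102, 114] | 108 | 108 | 102 + 6 = 108 | 0 |

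The earlier windows also have a gap of 0, including the first (0 + 8 = 8). Only (76, 90] fails. Week 82 is 2 weeks before the scan is due and 1 week before its allowed range of weeks 83 to 85 opens.

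**Step 3: compare visit assignment.** A scan at week 76 goes to week 72 in both sections. At weeks 76.5, 77 and 78 it goes to week 84 in 3.8.1.6.1 and to week 72 in 2.4.5. At week 78.5 it goes to week 84 in both.

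**Step 4: cross-check with the PRO windows.** SAP Table 3-6 follows the same 8- then 12-weekly schedule and ends the Cycle 19 window at day 547. With day = date − randomization + 1, that is (547 − 1)/7 = week 78.

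**Step 5: size.** Inputs from SAP 3.14 are: mutant-cohort accrual of 5, 14 and 24 per month (to month 6, months 6 to 12, thereafter), 340 patients, 1:1 allocation, median PFS 11.67 and 7.0 months, exponential; PFS looks at months 25 and 32. OS looks at months 45 and 54 are from SAP 3.15. A month is 30.4375 days (SAP 2.1.12).

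- Accrual: 6 × 5 + 6 × 14 = 114 by month 12; (340 − 114)/24 = 9.4 more months, so it ends at about month 21.4.
- Weeks 82 and 84 are 82 × 7/30.4375 = 18.86 and 84 × 7/30.4375 = 19.32 months.
- Progression-free at week 82: alpelisib 2^(−18.86/11.67) = 0.326; control 2^(−18.86/7.0) = 0.154; mean 0.240.
- Month 25: patients at weeks 82 to 84 were randomized at months 5.68 to 6.14, so 0.32 × 5 + 0.14 × 14 = 3.6 patients; 3.6 × 0.240 = 0.9 (about 0.6 alpelisib, 0.3 control).
- Month 32: randomized at months 12.68 to 13.14, so 0.46 × 24 = 11.0 patients; 11.0 × 0.240 = 2.6. By arm: 5.5 × 0.326 = 1.8 alpelisib and 5.5 × 0.154 = 0.9 control.
- Months 45 and 54: these patients would have been randomized after month 25, when accrual is over, so none.

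For patients whose observation ends at the cut-off these are upper figures, because anyone scanned after week 76 is not miscounted.

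**Step 6: effect on PFS.** Censoring uses 2.4.5: "Rule 3: if LATA happens after 68 weeks from randomization (the matched scheduled tumor assessment is C19D1 or later"). A LATA in (76, 78] is later than week 68 whichever visit it is matched to, so D1 = 12 + 2 = 14 weeks and D2 = 2 × 12 + 2 = 26 weeks either way.

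**The case against.** The strongest reply is that the text states its own intent. The at-risk clause explains itself as being ongoing when the scan is due, and a programmer who coded that meaning would wait until week 84, so no premature count would arise. This is fair: a false count is not certain. But the literal 6-week rule and its explanation disagree for this one window, and the SAP does not say which governs.

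A second reply is that week 76 keeps the week-72 window symmetric. That is true, but the next window then becomes 14 weeks wide, and a 6-week lead cannot reach its scan. One of the two windows has to be uneven. Letting it be (68, 78] keeps both at-risk points right.

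Third, scans in (76, 78] are already at least 3 weeks past the allowed range of 71 to 73, so they are off schedule under either section. This stands, and it limits the visit mismatch to a few late scans.

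A reader might infer more than the documents support:

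- **That everyone entering (76, 90] is miscounted.** With full follow-up, about 170 × 2^(−17.48/11.67) = 60 alpelisib and 170 × 2^(−17.48/7.0) = 30 control patients would be progression-free at week 76. But only about 51 patients in all could have reached week 76 by month 25, and about 175 by month 32. Entering the window is also not the same as being miscounted.
- **That about 3 false counts arise at any cut-off.** That needs accrual of 24 per month in the relevant two weeks. Of the four looks in Step 5, it holds only at month 32.
- **That the table would show a material false difference between arms.** At month 32 the difference is about one patient in 170 per arm.

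**Conclusion.** The inconsistency is real. It lies within SAP 3.8.1.6.1 and between that section and SAP 2.4.5, and the PRO windows side with week 78. Two groups are affected: patients without documented progression whose observation ends from week 82 up to week 84 with no scan since week 76, and scans falling in (76, 78].

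The effect is small: at most about 1 patient at the month-25 cut-off, about 3 at month 32 (about 2 alpelisib and 1 control), and none at months 45 or 54. These sizes assume the planned accrual, the planned look times and exponential PFS with the planned medians. Deaths, withdrawals or losses to follow-up in the same two weeks could add to them; the documents give no rate from which to count these.

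The consequence is confined to the descriptive missing-assessment table. A reader might infer that PFS censoring or the primary analysis is affected; it is not, because Rule 3 applies under either boundary. No alpha, power or sample-size figure is involved.

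**What to change.** In SAP 3.8.1.6.1, replace (68, 76] and (76, 90] with (68, 78] and (78, 90]. The at-risk points become 68 + 4 = week 72 and 78 + 6 = week 84, both equal to the scheduled scan. The second window is centered at (78 + 90)/2 = 84, and visit assignment then agrees with SAP 2.4.5. Add (68, 78] as an exception to the centering statement.

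The cost is one boundary value changed in the two windows and the matching program code, and a short added clause. The only drawback is that (68, 78] is centered at week 73 instead of 72, which is why the exception has to be written down.

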3.8.2 Secondary efficacy analyses

The analysis of all secondary efficacy endpoints will be performed, where appropriate, based on the FAS for i) cohort of patients with PIK3CA mutant status, and ii) cohort of patients with PIK3CA non-mutant status.

3.8.2.1 Key secondary objective: overall survival

The key secondary objective of the study are to determine whether treatment with alpelisib in combination with fulvestrant prolongs OS compared to treatment with placebo in the PIK3CA mutant cohort.

In the PIK3CA mutant cohort, a hierarchical testing procedure will be adopted and OS will be tested between the two treatment groups, provided the primary endpoint PFS is statistically significant favouring alpelisib.

OS is defined as the time from date of randomization to date of death due to any cause. If a patient is not known to have died by the date of analysis cut-off, then OS will be censored at the last contact date (see [Section 2.1.10](#)).

Assuming proportional hazards model for OS, the following statistical hypothesis for OS will be tested using a stratified log-rank test (according to randomization stratification factors) at the one-sided level of significance of 2.0%:

$$H_{02}: \theta_2 \geq 0 \text{ vs. } H_{a2}: \theta_2 < 0$$

where θ_2 is the log-hazard ratio (alpelisib-fulvestrant treatment arm vs. placebo-fulvestrant treatment arm) of OS.

The analysis for OS will be based on the FAS population according to the treatment arm patients were randomized to and the strata they were assigned to at randomization.

The final OS analysis will not be performed at the time point of the final PFS analysis in the PIK3CA mutant cohort, but after additional follow-up. Therefore, a three-look group sequential design is considered for OS, see Section 3.12.2 for further details.

The type I error probability will be controlled by using a separate Lan-DeMets (O'Brien-Fleming) alpha spending function independent of the Haybittle-Peto boundary used for the

primary efficacy analysis of PFS at a 2.0% level of significance. This guarantees the protection of the overall type I error ($\alpha = 2.5\%$) across all hypotheses and the repeated testing of the OS hypotheses at the interim and the final analyses ([Glimm 2010](#)). This includes hypotheses associated with the secondary endpoints PFS and OS in the *PIK3CA* non-mutant cohort (PFS in the non-mutant cohort will be tested at a 0.5% level of significance if PoC is established).

The OS distribution will be estimated using the Kaplan-Meier method, and Kaplan-Meier curves, medians and 95% confidence intervals of the medians along with the proportion of patients alive at 12, 24, 36, and 48 months will be presented for each treatment group. The hazard ratio for OS will be calculated, along with its 95% confidence interval, using a stratified Cox model using the same stratification factors as the log-rank test. The purpose of the two-sided 95% CI is to give an estimate of the respective treatment effect together with a comparable measure of reliability but not for reconstructing the test decisions.

Supportive Analyses

If the key secondary endpoint OS is statistically significant, a multivariate stratified Cox regression model will be fitted to evaluate the effect of other baseline demographic or disease characteristics on the estimated hazard ratio. This model will include the following key prognostic factors: ECOG performance status (0 vs. 1), bone lesions only at baseline (yes or no), number of prior lines of therapy in any setting (1st line vs 2nd line) and region (see [Section 3.13.2](#) for definitions).

All covariates will be included in the model regardless of their observed significance (p-value for given covariate).

If the analysis for OS is statistically significant, subgroup analyses of OS will be performed to explore homogeneity of the treatment effect across relevant patient subsets. See details in [Section 3.14.2](#).

The pattern of censored data will be examined between the treatment arms: reasons for censoring ('Alive' or 'Lost to follow-up') and death cause will be summarized by treatment arm. Survival status, reason for censoring and death cause will be listed. Patients not known to have died will be censored for 'Loss to follow-up' if the time between their last contact date and the analysis cut-off date is longer than 12 + 2 weeks = 98 days (i.e. the planned interval between two OS follow-up visits plus the 1 week window on either side).

If there are any COVID-19 related deaths, an additional sensitivity analysis on the FAS will be performed to address the potential impact of COVID-19 pandemic, censoring all deaths related to COVID-19 at the time of the event. The efficacy analyses for the key secondary endpoint OS in the *PIK3CA* mutant cohort; i.e. the stratified log-rank test, Kaplan-Meier estimates, estimate of the median OS along with 95% confidence interval, and hazard ratio obtained using the stratified Cox proportional hazards model, will be repeated.

Handling missing month/day in date of death

For rare cases when either day is missing or both month and day are missing for the date of death, the follow imputation rules will be implemented:

- If only day is missing, then impute max [(1 mmm-yyyy), min (any valid date from data base used for deriving last contact date +1, cutoff date)].
- If both day and month are missing, then impute max [(1 Jan-yyyy, min (any valid date from data base used for deriving last contact date +1, cutoff date)].

